1. An extended-release (30-day, “XR”), intramuscular injection of naltrexone (Vivitrol®). Studies on XR naltrexone have shown better long-term medication continuation compared to oral naltrexone and reduced heavy drinking days compared with placebos. Additionally, one meta-analysis showed a trend toward fewer admissions compared to oral naltrexone. One ongoing clinical trial is directly comparing oral to XR naltrexone for AUD in a safety-net hospital in Boston, and it is expected to evaluate the results in late 2020. Regardless, data from multiple centers and regions are needed, and our study uniquely targets high-utilizer patients.
2. A single infusion of intravenous ketamine, a dissociative anesthetic used in general anesthesia and pain management. At sub-anesthetic doses, ketamine provides rapid effects on mood that extend weeks beyond administration, and in 2019 the FDA approved an intranasal formulation for treatment-resistant depression. For AUD, treatment with ketamine decreased cravings and drinking at 10 days post-infusion in a human laboratory study that excluded patients with depression. In a recent randomized trial, AUD patients were given one ketamine infusion and subsequently showed a higher rate of abstinence at 21 days beyond treatment and better attendance at the final study visit compared to the control group (100% vs 74%, respectively), with no serious adverse events reported.

Both single-dose interventions hold great potential for improving AUD post-hospital transitions and reducing immediate re-admissions, but more data on feasibility and effectiveness are needed.

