### IV. Research Methods

#### A. Outcome Measure(s):

See table 1 for primary and secondary outcomes. In brief, our primary outcomes will be those related to feasibility as well as risk of 30-day all-cause hospital re-admissions. Secondary outcomes include risk of 30-day all-cause emergency department visit,

differences in readiness-to-change, and likelihood of having an alcohol metabolite (EtG) in the urine at follow-up.

*Table 1 Primary and secondary outcomes*

	Study Aim	Description	Instrument(s)
1' feasibility outcomes	1	Recruitment rate (# enrolled / month), follow-up rate, patient acceptability, adverse effects	Chart review, questionnaires
1' clinical outcome	2	Risk of 30-day all-cause hospital re-admissions	Chart review
2' clinical outcomes	2	Risk of 30-day all-cause ED visits	Chart review
	2	Within-subject difference in readiness-to-change 	Questionnaire
	2	Laboratory(+) for alcohol at SUDS	Urine EtG
	2	Percent of binge drinking days  since discharge	Questionnaire

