### ***Data Collection***

Data will be primarily collected at four time-points (Table 4). Data will be entered by staff into a REDCap database on tablet computers in the hospital and at SUDS clinic. Data collected at enrollment will primarily be descriptive, including demographics, recent drinking history, readiness to change, and various contributing factors to drinking. Immediately after intervention, vital signs,

symptoms, and acceptability will be recorded. Data collected on post-discharge arrival to SUDS clinic will include most 2' clinical outcomes. We will obtain re-admission rate (1' clinical outcome) through chart review, conducted by research team members at 30-days post-discharge.

Table 4 Patient flow and data collection points

Step	Who	Notes	Data collected – staff entered
Patient identified on consult list	ACS	Quick screen that meets inclusion criteria	
↓			
Addiction consult performed	ACS	Evaluation, withdrawal management, medication (though if patient consents to study, will not be prescribed an addiction medication at discharge), brief therapy, referrals, disease screening/harm reduction	
↓			
Screen, consent, randomization	ACS	Formal screen to identify any exclusion criteria. Simple randomization by algorithm	
 
• E-Consent (should include consent to see records in “care everywhere” – some hospitals require permission – when checking for ED visits and re-admissions)
 
• Screening documentation (inclusion and exclusion criteria)
 
• Alcohol-related admissions in last 12 months (date, location, top 3 diagnoses)
 
• Assigned group
 

↓			
Baseline data, referral to SUDS [data collection point #1]	ToD	ToD collects baseline data first, then performs “biopsychosocial intake” and sets up SUDS appointment within 1 week of discharge.  Discharge date is not always predictable;	
 
• Demographics
 
• Baseline clinical data
 
• Depression symptoms baseline (PHQ9 2 wks)
 
• Drinking History 7-days prior to admission (TLFB)
 
• Readiness to change (SOCRATES-8A)
 
• ACE Questionnaire
 

		ACS to review active hospitalized research participants and contact ToD/update date in RedCap as needed.	
↓			

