Intervention administered [data collection point #2]	RN, ACS	
For 'linkage-alone' group, data to be entered following consult.
 
For NTX group, intervention administered prior to discharge (could be same day as consent). Vitals immediately preceding and 40 min post- injection. Data collected after administration.
 
For KET group, intervention administered prior to discharge (could be same day as consent), though should have no food for at least 3 hours (~50% gastric emptying). Vitals immediately preceding, after completion, and 2 hours following end of intervention.
	
 
Vital signs (HR, BP, O2): linkage-alone group- baseline only, recorded after consult. NTX group- baseline, 40 min after administration. KET group- baseline, end of administration (~40min), 2 hours after end of administration.
 
Most recent AST, ALT
 
UDS-5 data
 
[for KET] Dissociative symptoms (CADSS) after administration (40 min)
 
[for NTX and KET] Acceptability of intervention (10-point Likert) after administration
 
[for NTX and KET] Readiness to change (SOCRATES-8A) after administration (40 min)
 
 
ORDER: CMP (if not already obtained), UDS-5 (if not already obtained)
 
ORDER in discharge orders (outpatient): CMP, UDS-5, urine EtG (if not already ordered)

↓			
Presentation to SUDS, data entered, contingency management reward administered [data collection point #3]	SUDS staff	
Upon presentation, staff to collect study data. After completion, will receive contingency management reward.
 
Then patient to complete standard intake/follow-up visit, if willing.
	
 
Drinking History since discharge (TLFB since discharge)
 
Depression symptoms (PHQ9 modified to read "since discharge.")
 
Readiness to change (SOCRATES-8A)
 
[for KET] Dissociative symptoms (CADSS)
 
Adverse Events (Modified PRISE)
 
Acceptability of intervention (10-point Likert)
 

		Staff to instruct patient to present to the clinic laboratory (e.g. pav G) for CMP after the visit.	
 
Contingency management feedback (10-point Likert, open ended)
 

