30-day chart review [data collection point #4]	Research staff	Should check encounters tab as well as “care everywhere” for Denver Metro region.	
 
Admissions (up to 5) within 30 days of discharge date (date, location, up to top 3 main diagnoses based on documentation available).
 
ED visits (up to 5) within 30 days of discharge date (date, location, up to top 3 main diagnoses based on documentation available).
 
AST, ALT obtained at SUDS f/u (if available)
 
Urine EtG obtained at SUDS f/u (if available)
 

Screening: The addiction consult team will attempt to screen patients meeting the inclusion criteria during inpatient admission. We anticipate 10 patients will meet inclusion criteria weekly. They will be assessed for clear exclusion criteria documented in the chart, and if none are noted the patient will be asked if they would like to join the study and complete the screening. If still no exclusion criteria are met and the patient expresses interest, they will be engaged in informed consent. The primary team will be notified by the addiction medicine team. Each combined process of screening and consent is anticipated to require 15 minutes at the end of a typical consultation. The screening window is anticipated to last 5 months.

Randomization: Patients will undergo a simple randomization algorithm to one of three arms.

Intervention:

- **Arm 1:** Receive a single dose of XR naltrexone (380mg) prior to discharge.
- **Arm 2:** Receive a single infusion of IV ketamine (0.5 mg/kg over 40 minutes) prior to discharge.
- **Arm 3:** No single-dose medication
- *All groups will receive enhanced linkage to care that includes contingency management, initiation of biopsychosocial intake, and appointment scheduling. This aspect alone surpasses the current standard of care.*

Contingency Management: Patients will receive a debit card prior to discharge from the hospital. We will utilize a pre-existing system - ClinCard by Greenphire. Participants will receive \$10 upon completion of baseline data, and \$20 upon completion of follow-up data (at SUDS clinic).

Follow up: Patients will be assigned a follow-up within 7 days of discharge at the outpatient addiction clinic (Denver Health SUDS clinic in pavilion K).

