#### **E. Potential Scientific Problems:**

One potential limitation is the small sample size. As a pilot study, our main aim is to test feasibility. A more robust, precise demonstration of clinical effectiveness will be pursued in a future project with data used from this study to inform sample size estimates as well as timelines.

Secondly, patients may be re-admitted to hospitals that do not show up in our medical record system (Epic). Insurance claims data would be ideal, but at this stage the added value does not justify the costs required for acquisition. Notably, Epic “Care Everywhere” can detect admissions in the University of Colorado Health system (12 hospitals in Colorado), SCL Health (5), and Centura Health (17). This network of hospitals provides high coverage based on our population, many of whom are homeless and located in a small regional geography.

Another potential limitation is a low follow-up rate at SUDS. This is one major reason for including contingency management as part of our enhanced linkage to care. Regardless, the primary quantitative outcome (hospital re-admission) will not require data from SUDS attendance to measure.

Alternative designs were considered but deemed beyond the scope of this proposal:

- “*Double dummy*” *placebos*, which can minimize bias in both researcher and participant. However, this would be personnel and time-intensive, and due to ketamine’s unique psychoactive effect, patients are unlikely to be successfully blinded.
- *2x2 factorial design*, which could gain information on combinations of multiple interventions, but would unnecessarily weaken inferences and complicate statistical analysis due to interactions in this small sample.
- *30-day in-person evaluation*, which would facilitate additional longitudinal measurement. However, we are not confident that enough patients would show up (or be reachable by telephone) to allow for meaningful analysis.

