#### **F. Data Analysis Plan:**

Participants’ demographic and baseline clinical data will be tabulated, and differences between groups will be assessed using a Fisher’s Exact Test for categorical variables and a two-sample t-test for continuous variables. These tests

will help evaluate the effectiveness of randomization. Feasibility outcomes (Aim 1) such as adverse events and acceptability (Likert scale) will be compared for each group using a Fisher's Exact Test and Wilcoxon-Mann-Whitney Test, respectively. Overall recruitment rate and follow-up rate will be tallied at the conclusion of data collection.

For Aim 2, all-cause hospital re-admission within 30-days of discharge will be recorded as a binary outcome. Rates of the two medication intervention groups (XR naltrexone or IV ketamine) will be compared against the group that received enhanced linkage to care alone.

This pilot study may not be sufficiently powered for robust hypothesis testing. By one crude estimate, we could have approximately 80% power to detect a difference between a medication group and the linkage-alone group with about 60 participants assuming a re-admission rate is 25% vs 15%. A larger effect size would increase our power and/or reduce the number of participants required. Regardless, this will provide parameter estimates that can inform a future sample size calculation in a larger effectiveness trial.

For further descriptive purposes, a secondary utilization outcome is risk of 30-day all-cause ED visits. This will be evaluated in a similar manner as hospital re-admissions. Additionally, we are interested in the within-subject difference in readiness-to-change. For those who follow-up, a mean of pre/post differences will be calculated, and a paired t-test will be used to determine if the null hypothesis ( $H_0$ : difference = 0) can be rejected. Drinking behavior will be measured using the Timeline Follow Back method. Binge drinking will be defined as 5+ drinks for men, 4+ for women, and the proportion of binge drinking days since discharge will be calculated for each group. Proportions of positive urine ethyl glucuronide (EtG) will also be tabulated for each group.

Data will be analyzed in SAS.

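### EtG and binge-day results by arm exist only for clinic attenders, so differences between arms are not randomized comparisons and may be biased in either direction

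*Combined protocol and SAP*

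**What the plan says.** Table 1 (section IV.A) lists two drinking measures as secondary clinical outcomes under Aim 2: EtG, defined as "Laboratory(+) for alcohol at SUDS", and percent of binge drinking days since discharge. Section IV.C (Data Collection) states: "Data collected on post-discharge arrival to SUDS clinic will include most 2' clinical outcomes". In Table 4 the post-discharge Timeline Follow Back (TLFB) is taken at the SUDS visit, and the 30-day chart review picks up the SUDS EtG result only where one is available.

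Section IV.F analyses them in two sentences. For binge days, "the proportion of binge drinking days since discharge will be calculated for each group". For EtG, "Proportions of positive urine ethyl glucuronide (EtG) will also be tabulated for each group". It states no denominator, no rule for patients without a visit or sample, and no sensitivity analysis. The follow-up rate is to be tallied overall; a split by arm is not specified.

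Section I presents both drugs as suited to improving treatment retention. Section II reports that patients given ketamine in a cited randomized trial showed "better attendance at the final study visit compared to the control group (100% vs 74%, respectively". Section IV.E concedes: "Another potential limitation is a low follow-up rate at SUDS". It offers contingency management in response and notes that re-admission can be measured without SUDS data. It does not discuss follow-up that differs between arms.

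**The concern.** Randomization makes the arms comparable as randomized. It does not make the attenders in one arm comparable with the attenders in another when treatment may affect who attends. If a drug brings in patients who would otherwise have stayed away, and those patients drink more or less than the rest, the arms will differ on EtG and binge days even if the drug does nothing to drinking. Because follow-up is tallied only overall, a reader of the tables might not see the attendance difference that would warn of this.

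EtG is the only laboratory measure of drinking among the listed outcomes, and the pilot is meant to inform a larger effectiveness trial. A misleading difference here could affect which arm is taken forward or what effect is expected.

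**Working it through.** **Inputs from the documents**
- Attendance in the cited ketamine trial: 100% vs 74% (section II).
- Local clinic follow-up: 11.8% (section II). Section III gives 2 of 17, and 2/17 = 11.8%, so the figure is reproduced.
- 45-60 participants in three arms (section IV.C), so 15-20 per arm if allocation is equal (assumed).
- The plan has no calculation for EtG or binge days, so there is no design figure to reproduce.

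**Assumed.** All drinking rates below are illustrative; the documents give none for attenders or non-attenders.

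**Step 1: the bias for a drug with no effect on drinking.** Let A_L and A_D be attendance under linkage alone and on the drug. Assume that anyone who would attend under linkage alone would also attend on the drug. Let a be the EtG-positive proportion in those patients and n the proportion in everyone else. Linkage attenders show a. Drug attenders show [A_L·a + (A_D − A_L)·n]/A_D. The difference, drug minus linkage, is (1 − A_L/A_D)(n − a). At 74% and 100% this is 0.26(n − a).

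| a | n | Linkage attenders | Drug attenders | Difference (points) |
|---|---|---|---|---|
| 50% | 70% | 50.0% | 55.2% | +5.2 |
| 50% | 90% | 50.0% | 60.4% | +10.4 |
| 30% | 90% | 30.0% | 45.6% | +15.6 |
| 50% | 50% | 50.0% | 50.0% | 0 |
| 50% | 30% | 50.0% | 44.8% | −5.2 |

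The same model can start from a common true proportion p in both arms. Linkage attenders then show a = (p − 0.26n)/0.74, and the drug arm shows p.
- p = 60%, n = 80%: (0.600 − 0.208)/0.74 = 53.0%, difference +7.0.
- p = 60%, n = 100%: (0.600 − 0.260)/0.74 = 45.9%, difference +14.1.
- p = 40%, n = 80%: (0.400 − 0.208)/0.74 = 25.9%, difference +14.1.
- p = 40%, n = 100%: (0.400 − 0.260)/0.74 = 18.9%, difference +21.1.

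The direction depends only on the sign of n − a. For binge days the same formula applies with mean percentages in place of proportions.

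**Step 2: attendance nearer the local rate.** Suppose linkage attendance is 11.8% and the drug adds the same 26 points (37.8%). With a = 50% and n = 90% the difference is (1 − 0.118/0.378) × 0.40 = +27.5 points; with n = 30% it is −13.8. If the drug keeps the 100:74 ratio instead (15.9%), the first case returns to +10.4. An arm attending at 11.8% would contribute only 15 × 0.118 = 1.8 to 20 × 0.118 = 2.4 patients.

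**Step 3: at this trial's size.** In a simulation of 400,000 trials (20 per arm, 74% vs 100%, a = 50%, n = 90%), the drug with no effect looked worse in 72% and better in 26%. With n = 50% the split was 49% and 49%.

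**Step 4: what simple repairs do (74% vs 100%).**
- *Missing counted as positive.* Linkage becomes 0.74a + 0.26 and the drug arm stays at 0.74a + 0.26n, a difference of −0.26(1 − n). This is −2.6 points at n = 90% and −13.0 at n = 50%, a false benefit.
- *Attended and EtG-negative, over all randomized.* This is the complement of the previous measure and carries the same bias. At p = 60%, n = 80% it gives 40.0% on the drug against 0.74 × (1 − 0.530) = 34.8% on linkage, a false benefit of 5.2 points.
- *Best- and worst-case bounds.* With a = 50%, n = 90%, linkage ranges from 0.74 × 0.50 = 37.0% to 37.0 + 26.0 = 63.0%, and the drug arm is fully observed at 60.4%. The difference runs from 60.4 − 63.0 = −2.6 to 60.4 − 37.0 = +23.4 and contains the true value, 0. The width equals the sum of the two missing proportions: 26 points here, but 88.2 + 88.2 = 176.4 points if both arms attended at 11.8%.

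**The case against.** The plan tests nothing on EtG or binge days. It tabulates them in a paragraph introduced as descriptive, the Aim 2 hypothesis concerns re-admission, and Table 1 already defines EtG as a result at the clinic. The restriction to follow-up attenders is written only for readiness-to-change; for the drinking outcomes the denominator is simply unstated. Contingency management is given to every arm and is aimed at the very attendance that produces these data. Sampling error also exceeds the bias. With 20 per arm, p = 60% and n = 80%, the 95% half-width is 1.96 × √(0.60 × 0.40/20 + 0.53 × 0.47/14.8) = 33 points; at p = 40%, n = 100% it is 29.

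Much of this stands and limits the weight of the point. It does not remove it. The data source restricts both outcomes to attenders whatever the text says. By-arm tables of outcomes listed under Aim 2 invite a comparison between arms. Offering the same incentive to all arms does not make attendance equal. Imprecision shows as a wide interval, whereas selection does not show at all unless attendance is reported by arm.

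A reader might go further and infer that the plan will make ketamine look worse than linkage alone. The documents do not support that. It requires non-attenders to drink more than attenders, and no figure on this is given. The 100% vs 74% is one other trial's final study visit, not a SUDS visit under contingency management, and the documents give no attendance figure for naltrexone.

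**Conclusion.** The concern holds as a gap in analysis and reporting. By-arm EtG and binge-day figures are conditional on a post-randomization event that the plan expects treatment to influence, and section IV.F provides neither by-arm attendance nor any handling of the missing patients. Differences between arms in these tables cannot be read as randomized comparisons.

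Size and direction are open. At 100% vs 74% attendance and no drug effect on drinking, the illustrative cases run from about −5 points (non-attenders drink less), through 0 (attendance unrelated to drinking), to about +21 points (non-attenders drink much more). These rest on assumed drinking rates and on attendance borrowed from the cited trial.

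The outcomes are secondary and untested in a pilot, and the primary clinical outcome does not depend on clinic attendance. The change is worth making because it is nearly free and the pilot's figures are meant to inform a larger trial.

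**What to change.** Add to section IV.F:

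1. Report by arm, over all randomized patients, the number attending SUDS, the number with an EtG result and the number with a post-discharge TLFB record. Put these beside the attender-only EtG and binge-day percentages, and label those percentages as conditional on attendance and not a randomized comparison.
2. For EtG, give full best- and worst-case bounds for each drug-minus-linkage difference over all randomized patients: missing counted as positive in the drug arm and negative in linkage, then the reverse. Missing counted as positive in all arms may appear as one sensitivity row only, with a note that it favours the better-attending arm. For the same reason, do not present the proportion attended and EtG-negative as a stand-alone effect on drinking.
3. Describe attenders against non-attenders on the 7-day pre-admission TLFB already collected at baseline. Do not add model adjustment: with at most about 20 patients per arm it would be fragile, and it cannot remove selection on drinking after discharge.

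The cost is a few table rows and no new data. If attendance stays near the local 11.8%, the bounds will be too wide to inform. That would itself be a useful finding for the larger trial.

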## **F. Summarize Knowledge to be Gained:**

We hope to demonstrate feasibility of two single-dose interventions given in the hospital setting and estimate their effects in terms of hospital readmissions. The knowledge gained will help inform a future, larger comparative effectiveness study. The data will also help CAM staff related to tracking and incentivizing transitions of care for patients with AUD.

